Given these shortcomings in this evolving area of clinical research, a comprehensive characterization of myocardial injury in patients with COVID-19 infection and the identification of clinical predictors for its occurrence could allow the development of predictive models, thus helping clinicians in the disease phenotyping and the early assessment of the risk of unfavourable outcome and improving a fast determination of most appropriate treatments and clinical paths, efficient planning and use of clinical resources in terms of treatment type and units (such as intensive care or coronary intensive care). In addition, the identification of clinical predictors and/or protective factors for myocardial injury in COVID-19 infection may pave the way for the development of specific therapeutic strategies aiming to reduce the impact of myocardial injury on COVID-19-related morbidity and mortality. Finally, assessing the long-term cardiovascular impact of myocardial injury in COVID-19 infection could help clinicians in the prognostic stratification and the choice of therapeutic strategies in the post-acute COVID-19 phases, possibly identifying those patients that may need a more aggressive therapy and a closer follow-up.

A comprehensive characterization of myocardial injury in COVID-19 infection is still lacking, and no clinical predictors of myocardial injury has been identified yet. Moreover, the long-term cardiovascular outcome of myocardial injury in the post-acute COVID-19 phase is largely unknown. We thus hypothesize that:

- that clinical predictors and/or protective factors (including vaccination status) for myocardial injury in COVID-19 infection could be identified, thus allowing the development of predictive models that could help clinicians in the disease phenotyping,

the early assessment of the risk of unfavourable outcome and improving a fast determination of most appropriate management;

- that myocardial injury in COVID-19 patients could be associated with a worse clinical course characterized by higher incidence of in-hospital complications and need for escalation of therapies;
- that myocardial injury in COVID-19 patients could be associated with a worse angina status and quality of life as well as with a higher rate of adverse cardiovascular events in the post-acute COVID-19 phase, thus helping in the prognostic stratification of COVID-19 patients and identifying those that may need a more aggressive therapy and a closer follow-up.

OBJECTIVES

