Primary objective

To identify clinical predictors of myocardial injury in patients hospitalized for COVID-19 infection since the introduction of vaccines (i.e., March 1, 2021).

Secondary objectives

1. To evaluate if the presence of myocardial injury during the index hospitalization for COVID-19 is associated with a worse in-hospital clinical course in terms of in-hospital complications and need for aggressive therapies.
2. To evaluate if the presence of myocardial injury during the index hospitalization for COVID-19 are associated with a worse angina status and quality of life (evaluated using the Seattle Angina Questionnaire [SAQ] summary score (15)) at 12-months follow-up.
3. To evaluate if the presence of myocardial injury during the index hospitalization for COVID-19 predicts a worse clinical outcome in terms of major adverse cardiovascular events (MACE) (defined as the composite of cardiovascular death, ischemic heart disease [acute or chronic coronary syndromes], stroke/transient ischemic attack [TIA] and hospitalization for heart failure), dysrhythmias (defined as the composite of new-onset atrial fibrillation and/or ventricular arrhythmias), inflammatory heart disease (pericarditis and/or myocarditis) or thrombotic disorders (pulmonary embolism, deep vein or superficial vein thrombosis) at 12-months follow-up.

METHODS

Study design

Retrospective and prospective observational study.

Population

All consecutive patients hospitalized at Policlinico Universitario A. Gemelli IRCSS since March 1, 2021, with a diagnosis of SARS-CoV-2 infection (≥ 1 positive nasopharyngeal swab) and at least one value of high-sensitivity cardiac troponin I (hs-cTnI) measured during the index hospitalization will be enrolled. Given that the patients are unable to physically sign the informed consent form due to epidemiological reasons (contamination of papers by SARS-CoV-2), each patient will verbally declare the consent to “Consenso al trattamento dei dati personali e dei campioni biologici a scopo di ricerca – no profit”, “modulo di dichiarazione della volontà espresso ai fini del consenso informato generale alle cure” and “modulo dossier sanitario – richiesta di oscuramento/deoscuramento di eventi/episodi” at the presence of at least two witnesses.

Inclusion criteria

- Age ≥ 18 years;
- Overt COVID-19 infection (molecular nasopharyngeal swab positive for SARS-CoV-2 ≥ 1);

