- Patient with at least a high sensitivity Troponin I measured during hospitalization course.
- Available data on vaccination.
- Verbal informed consent

Exclusion criteria

- Age <18 years;
- Patient in whom at least one high sensitivity Troponin I value measured during the course of hospitalization is not available.
- No data available on vaccination status.

Variables and procedures

This study will make use of Data Mart COVID-19 developed within Generator Real World Data Unit. The Data Mart COVID-19 belongs to the family of the diagnostic and prognostic mini-bots developed within the Generator Real World Data Unit project in which artificial intelligence solutions (such as text mining) are adopted to automatically extract both structured and unstructured data from hospital databases of patients infected from SARS-CoV-2. Feature selection and machine learning algorithms can be applied to develop diagnostic and prognostic support systems for clinicians.

The specific data that which will be exploited are:

- Demographics data;
- Patient comorbidities, vital signs and symptoms at the time of admission;
- Laboratory analysis;
- In-hospital complications (e.g.: need for non-invasive or invasive ventilation, access to intensive care unit, length of hospitalization, use of glucocorticoids or antibiotics, death);

- Blood gas exchange information;
- Radiological reports;
- Medications at the time of admission, during hospitalization and at the time of discharge;
- Vaccination status.

Clinical follow-up

All patients will undergo a clinical follow-up by telephonic interview and/or clinical visit at 12 months from hospital discharge, during which the incidence of MACE, dysrhythmias, inflammatory heart disease and/or thrombotic disorders (both as incidence of the composite and as incidence of each individual components) in the past months will be investigated, the SAQ will be administered and the SAQ summary score will be collected.

ENDPOINTS

Primary endpoint

To assess for the presence of clinical predictors for the occurrence of myocardial injury, defined as at least one value of hs-cTnI >99th percentile upper reference limit (16), in patients hospitalized for COVID-19 infection.

Secondary endpoints

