1. The occurrence of myocardial injury during the index hospitalization for COVID-19 infection will be correlated with in-hospital complications (defined as the composite of the need for non-invasive or invasive ventilation, access to intensive care unit, length of hospitalization, use of glucocorticoids or antibiotics, and death).
2. The occurrence of myocardial injury in patients during the index hospitalization for COVID-19 infection will be included in a prediction model and correlated with future cardiovascular events (MACE), dysrhythmias, inflammatory heart disease and/or thrombotic disorders at 12-months follow-up.
3. The occurrence of myocardial injury during the index hospitalization for COVID-19 infection will be correlated with angina status and quality of life, evaluated using the SAQ summary score, at 12-months follow-up.

STATISTICAL ANALYSIS PLAN

Sample size calculation

A comprehensive characterization of myocardial injury in COVID-19 infection is still lacking, and no clinical predictors of myocardial injury has been identified yet. Moreover, the long-term cardiovascular outcome of myocardial injury in the post-acute COVID-19 phase is largely unknown. Thus, this configures as a pilot study on large-scale cohort. As such no formal sample size calculation is needed. However, based on the COVID-19 datamart of our clinical institution and on inclusion criteria, we expect to include in the study around 2000 patients hospitalized with COVID-19. Such a sample size is largely consistent with common rules of thumb for pilot studies. In addition, the estimated sample size is largely consistent with the van Smeden metamodels related to the new statistical approaches for the development of clinical prediction models (17). The square root of the mean squared prediction error (rMPSE) and mean absolute prediction error (MAPE) may be approximated via the results of these. Lower values for rMSPE and MAPE indicate better performance. For instance, at a sample size of $N=400$, with $P=8$ candidate predictors and an expected event fraction of $\frac{1}{4}$, the predicted out-of-sample rMPSE would be 0.065 when ML model (without variable selection) is applied, and 0.053 for Ridge regression; MAPE would instead be 0.045 for the ML model and 0.038 for the Ridge regression.

Statistical analysis

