All demographic, clinical and laboratory characteristics will be summarized by descriptive statistics techniques. In depth, qualitative variables will be expressed by absolute and relative percentage frequencies. Quantitative variables, indeed, will be reported either as mean and standard deviation (SD) or median and interquartile range (IQR), respectively in the case they were normally or not normally distributed. Their distribution will be previously assessed by the Shapiro Wilk test. Between groups differences in the demographic, clinical, laboratory and pathologic features will be assessed by the Chi Square or the Fisher's exact test as for qualitative variables, with Yates correction, as appropriate, whilst quantitative variables will be evaluated either by the Student's t test or the Mann-Whitney U test, according to their distribution. Univariable and multivariable logistic regression models will be performed to evaluate the presence of clinical predictors for the occurrence of myocardial injury in COVID-19 infection. Results will be expressed as odds ratio (OR) with 95% confidence interval (CI). Model calibration performances will be evaluated via the Hosmer-Lemeshow goodness of fit test with 10 groups. Model performance will be assessed through receiver-operator characteristic (ROC) curve analysis by reporting the area under the curve, sensitivity, specificity and +/- likelihood ratio (LR). Univariable and multivariable logistic regression analysis will be performed also to assess the association of myocardial injury in COVID-19 infection with in-hospital complications and need for aggressive therapies.

Univariable and multivariable multiple linear regression will be instead used to assess

whether SAQ summary score at 12-months follow-up is affected by myocardial injury in patients with COVID-19 infection.

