All RWD studies have research purposes and therefore consent-related procedures are consistent with European Directive 2016/679. The data architecture which supports RWD studies has been defined to provide the highest degree of protection, in accordance with all GDPR and security requirements. In this respect, RWD provides “protection by design” in each step of the process.

Significance and innovation

This study will provide a detailed characterization of myocardial injury in patients with COVID-19 and its role in determining the different clinical courses of SARS-CoV-2 infection. Moreover, the aim of study is to identify, for the first time, the clinical predictors of the occurrence of myocardial injury in patients with COVID-19 infection that could allow the development of predictive models as well as help clinicians in the early assessment of the risk of myocardial injury and the prevention of the associated unfavourable outcomes. Furthermore, this study will characterize the cardiovascular outcomes in the post-acute COVID-19 phase, and it will evaluate for the first time the long-term clinical outcomes of patients who experienced myocardial injury, possibly paving the way for the implementation of specific therapies aiming to reduce the cardiovascular risk and the long-term sequelae of COVID-19.

References

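### Secondary endpoint 1 relates injury at any time in the stay to complications of the same stay with no time order, so its odds ratio shows co-occurrence only

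*Protocol*

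**What the plan says.** **Exposure.** The protocol's Primary endpoint section defines myocardial injury: "defined as at least one value of hs-cTnI >99th percentile upper reference limit". The Inclusion criteria require one troponin value at some point of the stay. They set no admission value, sampling schedule or time window.

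**Outcome.** Secondary endpoints, item 1, reads "The occurrence of myocardial injury during the index hospitalization for COVID-19 infection will be correlated with in-hospital complications". The complications are a composite of non-invasive or invasive ventilation, intensive care access, "length of hospitalization, use of glucocorticoids or antibiotics, and death". All belong to the same stay as the exposure.

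**Method.** Under Statistical analysis: "Univariable and multivariable logistic regression analysis will be performed also to assess the association of myocardial injury in COVID-19 infection with in-hospital complications". Cox models are planned only for the 12-month outcomes.

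**Purpose.** Secondary objective 1 asks whether injury "is associated with a worse in-hospital clinical course in terms of in-hospital complications and need for aggressive therapies". The matching hypothesis says that injury "could be associated with a worse clinical course characterized by higher incidence of in-hospital complications and need for escalation of therapies". Significance and innovation adds that the study will characterize injury and "its role in determining the different clinical courses of SARS-CoV-2 infection".

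**The concern.** The flag is set over the whole stay and the complications are counted over the same stay. A troponin value that first rises after intubation is recorded as injury associated with intubation, exactly as if it had risen before.

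Three mechanisms can move the odds ratio away from 1 with no effect of injury on the later course:

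- **Reverse order.** The complication raises the chance of a later positive troponin.
- **Longer stay.** A complicated stay leaves more days for a first positive value. Length of hospitalization is itself an outcome component, so part of the association is structural.
- **Early death.** A patient who dies early may have fewer troponin tests and so less chance of a positive one. This works in the opposite direction.

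Adjusting for other covariates does not restore the order of events. At stake is the interpretation: a clear odds ratio could be reported as showing that injury leads to a worse hospital course, which the planned analysis cannot establish.

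**Working it through.** The protocol gives no figure for this endpoint, so there is none to reproduce. From the document come N of about 2000 and two-sided p<0.05. **Every other input is an assumption. No true effect of injury is assumed, results are unadjusted, and the event is a generic early complication.** The full composite cannot be modelled, because the protocol gives no complication rates, stay lengths or testing frequency.

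**1. Reverse order (closed form).** Assume 15% are injured at admission, and 30% of the others turn positive after a complication.

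P(injury | complication) = 1 − 0.85 × 0.70 = 0.405, odds 0.405/0.595 = 0.681.

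P(injury | no complication) = 1 − 0.85 × (1 − late), where late is the share of initially negative, complication-free patients who turn positive later.

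| late | P(injury, no complication) | OR |
|---|---|---|
| 0 | 0.150 | 3.86 |
| 0.10 | 0.235 | 2.22 |
| 0.20 | 0.320 | 1.45 |
| 0.25 | 0.3625 | 1.20 |
| 0.30 | 0.405 | 1.00 |

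The chance of p<0.05 at N = 2000 (Wald test on the log OR) depends on how common complications are:

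| OR | 20% | 30% | 50% | 90% | 95% |
|---|---|---|---|---|---|
| 1.45 | 89% | 95% | 98% | 64% | 39% |
| 1.20 | 35% | 44% | 50% | 21% | 13% |

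Example, OR 1.446 with 30% complications: SE = √(1/(600 × 0.405 × 0.595) + 1/(1400 × 0.32 × 0.68)) = 0.101; z = 0.369/0.101 = 3.65; P(Z > 1.96 − 3.65) = 95%.

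**2. Longer stay alone (simulation, 1000 runs, N = 2000).** Assume 30% complications between day 0.5 and day 5.5; stay of max(6, 1 + geometric with mean 8) days; a further geometric time with mean 8 if complicated; 15% injured at admission; and no rise in risk after the complication.

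| Daily risk of first positive | OR | p<0.05 in |
|---|---|---|
| 1%, whole stay | 1.35 | 78% |
| 0.5%, whole stay | 1.21 | 36% |
| 0.25%, whole stay | 1.12 | 14% |
| 1%, first 10 days only | 1.09 | 13% |
| 1%, first 7 days only | 1.02 | 6% |

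At 1% per day over the whole stay, but with 90% or 95% of patients having a complication, p<0.05 occurs in about 36% and 21%. If the daily risk also doubles after the complication (30% complications), the OR is 2.06 and p<0.05 in 100%. With neither mechanism the OR is 1.00. A landmark at day 1, among patients still free of the complication, gives OR 0.99 to 1.01 in these set-ups, with p<0.05 in about 4% to 6%.

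A second set-up has no injury at admission, a constant injury rate tuned to 25% injured, 26% complications and a 10-day base stay. Prolonging complicated stays by a factor of 1.5 or 2 alone gives OR 1.61 and 2.26. The time-ordered rate ratio stays at 0.99 to 1.01. The size is thus set by the inputs.

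**3. Early death.** Assume 10% positive per test, one test in early deaths and three in others, with within-patient correlation ρ (beta-binomial).

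| ρ | P(ever positive, 3 tests) | OR, 1 v 3 tests |
|---|---|---|
| 0 | 0.271 | 0.30 |
| 0.3 | 0.208 | 0.42 |
| 0.6 | 0.158 | 0.59 |
| 0.9 | 0.114 | 0.87 |

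For ρ = 0: 1 − 0.9³ = 0.271; OR = (0.100/0.900)/(0.271/0.729) = 0.30.

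**The case against.** **The wording is associational throughout.** The hypothesis, objective, endpoint and analysis text all speak of association or correlation. Objective 3, which speaks of prediction, does get time-to-event models. This stands: the planned odds ratio answers objective 1 as co-occurrence and is not invalid for that purpose.

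**A reader might infer that the protocol commits itself to a causal or prognostic claim from this endpoint.** The text does not support that. The phrase about a determining role is a general statement of significance. It names no endpoint and is not confined to the hospital stay. The mention of early risk assessment in the hypotheses belongs to the hypothesis on predictors of injury, which is the primary objective. What remains is that the general wording could invite the stronger reading, and nothing in the planned in-hospital analysis could bear it.

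**A reader might also infer that the odds ratio will be inflated by a known amount.** It need not be. The illustrations run from below 1 to well above 1. The larger longer-stay results need a risk that persists through the stay, and the modelled event is not the protocol's composite. The landmark's clean result is partly built in, since every simulated stay lasts at least 6 days and nobody leaves before day 1.

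**A separate SAP could add a time window.** It could, but the protocol itself fixes the flag, the composite and the logistic model. The point concerns that stated choice, not an omitted detail.

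**Conclusion.** The point holds as a limit on interpretation, and a cheap improvement is available. As written, secondary endpoint 1 shows that injury and complications occur in the same stays. It does not show that injury comes first, forewarns of a worse course or determines it.

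The true size and direction of the artefact are unknown. With no true effect and the assumptions above, reverse order gives OR 1.0 to 3.9. Longer stay alone gives about 1.02 to 1.35 in the main set-up, with p<0.05 in about 6% to 78% of studies at N = 2000 and 30% complications. Unequal testing in early deaths can give an OR below 1. These figures illustrate what could happen; they do not estimate the bias in the planned multivariable result. The absence of time order rests on the protocol's definitions alone and needs none of these assumptions.

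**What to change.** For secondary endpoint 1 only:

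- Keep the planned logistic analysis and label its result as co-occurrence during the stay.
- Add one time-ordered sensitivity analysis for ventilation, ICU access and death. Either define injury from hs-cTnI in a fixed early window and count only events that start after it, or enter injury as a time-dependent covariate in time-to-event models, with discharge and death as competing events.
- Base any statement about the subsequent in-hospital course on that analysis.
- Report glucocorticoid and antibiotic use as co-occurrence only, since a large share may have started before or within an early window.
- If time stamps cannot be obtained, limit the conclusion and the wording in Significance and innovation to association.

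**Cost.** Some analysis text, and extraction of times for troponin values and complications. Variables and procedures says that the data mart will "automatically extract both structured and unstructured data from hospital databases"; that usable time stamps are among these data is an assumption. In the landmark version, patients drop out if they have no troponin value in the window, die or are discharged within it, or have already had the event. Its exposure also becomes early injury rather than any injury in the stay.

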Finally, to assess whether the presence of myocardial injury during COVID-19 predicts a worse outcome, in term of both MACEs at 12 months and single components, uni- and multivariable interaction proportional hazard Cox regression models will be computed. We will consider, as for MACEs, time to first event, and for each component, time to each event. To evaluate combined effects between each clinical/laboratory predictor and presence/absence of Myocardial Injury (MI), multivariable interaction Cox models will be fitted, and the interaction hazard ratios (IHR) evaluated. In particular, for each predictor, one interaction Cox model will be fitted. In this framework, IHR = 1 indicates no synergy between predictor and MI, IHR <1 expresses a reduction of hazard due to the synergy, while IHR >1 an increased hazard. The interaction parameters (IHR) will be interpreted as difference (in HR terms) of the predictor and MI (absence of MI as reference category). Proportionality of the hazard functions will be assessed by visual inspection of hazard plots and Schoenfeld residuals. When proportionality was doubtful, weighted Cox regression models would be fitted.

A two-tailed analysis will be performed and a p value <0.05 will be considered as statistically significant. Statistical analyses will be performed using R software version 4.2.1 (CRAN®, R Core 2021) (and its packages *survival*, *survminer*, *coxphw* and *Hmisc*) (18).

Data privacy and data protection

Privacy issues related to this project have been analyzed with Policlinico Gemelli Data Protection Officer (D.P.O.). As a GENERATOR RWD study, this project will be compliant with GDPR Italian and European directives and regulation (EU Directive 2016/679 and under Italian Laws: Decreto Legislativo 196/2003, Decreto Legislativo 101 2018, Autorizzazione Generale Garante 9/2016)

The guidelines for data privacy are covered by two main documents prepared with the D.P.O.:

- Generator main document “Linee Guida Utilizzo Real World Data” which prescribes the governance mechanisms for Generator through two main bodies (Comitato di Supervisione and Comitato Operativo) where representatives appointed from IRCSS and other key Units of Policlinico participate and have mandate to decide;
- “Orizzonte Normativo Real World Data” prepared by the D.P.O., which provides the directives for the execution of any Generator study to assure its compliance with European and Italian GDPR directives.

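### Secondary endpoint 1 puts length of hospitalization, a duration with no cut-off, into a composite analysed by logistic regression, so the composite has no yes/no value as defined

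*Protocol*

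**What the plan says.** Item 1 of Secondary endpoints correlates myocardial injury during the index stay with in-hospital complications, defined as a composite. After the need for ventilation, its components are "access to intensive care unit, length of hospitalization, use of glucocorticoids or antibiotics, and death". The data list under Variables and procedures gives the same items, introduced there as examples: "access to intensive care unit, length of hospitalization, use of glucocorticoids or antibiotics, death". Neither place states a number of days or defines a prolonged stay.

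The Statistical analysis section uses univariable and multivariable logistic regression for the "association of myocardial injury in COVID-19 infection with in-hospital complications and need for aggressive therapies". The other regression models go to other outcomes:

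- For the SAQ summary score at 12 months: "Univariable and multivariable multiple linear regression will be instead used to assess" the effect of injury.
- For the 12-month events: "in term of both MACEs at 12 months and single components, uni- and multivariable interaction proportional hazard Cox regression models will be computed".

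The same section plans Student's t or Mann-Whitney U tests for quantitative variables between groups, without tying them to this endpoint.

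**The concern.** Logistic regression models the odds of a binary outcome. A composite can be binary only if each component is an event that a patient either has or does not have. Ventilation, intensive care access, drug use and death meet that condition. Length of stay does not, because every hospitalized patient has one.

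At stake is the composite odds ratio for secondary objective 1. Until a rule is stated, two analysts working from this protocol could code the endpoint differently and both claim to follow it. The design makes timing relevant. The study is described as "Retrospective and prospective observational study" and draws on an existing data mart, so a rule set late could be set with outcomes already visible.

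**Working it through.** The protocol gives no event rate, cut-off or power for this endpoint, so there is no stated figure to reproduce. The check is one of logic.

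**Inputs**

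- Outcome: one composite that includes a duration (Secondary endpoints, item 1).
- Model: logistic regression (Statistical analysis).
- Population: inpatients only (Population).
- Expected size: about 2000 (Sample size calculation).

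**Three possible readings of the duration**

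1. Any stay counts. All of about 2000 patients are events. The odds are n/0 in both the injured and the uninjured group, so the odds ratio cannot be estimated.
2. The duration is ignored. The model can be fitted, but the outcome is no longer the composite that the endpoint defines.
3. A cut-off c applies. The model can be fitted, but c is not given.

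**How much the third reading leaves open**

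Let r be the proportion of patients with at least one of the other components. The composite is positive if another component occurs or stay exceeds c, so r ≤ composite rate ≤ 100%. The upper limit is reached at c = 0 and the lower limit as c becomes very large. This bound needs no assumption.

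For illustration only, assume r = 31.25%, log-normal stay with median 9 days and log-SD 0.7, and independence of stay from the other components. None of these figures is in the protocol, and the values of c are not proposals. Then

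rate(c) = 1 − (1 − r) × P(stay ≤ c), with P(stay ≤ c) = Φ[ln(c/9)/0.7].

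- c = 7: P(stay ≤ 7) = 0.3598; 1 − 0.6875 × 0.3598 = 75.3%.
- c = 28: P(stay ≤ 28) = 0.9475; 1 − 0.6875 × 0.9475 = 34.9%.
- c = 10, 14 and 21 give 61.5%, 49.4% and 39.0%.

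On these inputs the event fraction more than halves across the cut-offs, so the choice is not a minor coding detail.

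**Whether another planned analysis supplies the rule**

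Linear regression is named for the SAQ score and Cox regression for the 12-month events. The t and Mann-Whitney tests could compare stay between injured and uninjured patients, but they do not turn stay into a component of a binary composite.

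**A point that constrains the repair**

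The Primary endpoint section defines injury as at least one hs-cTnI value above the 99th percentile limit at any time in the stay. A longer stay gives more opportunity to record such a value. A patient first positive on day 10 must have remained in hospital for ten days to be classed as injured. A time-to-discharge model that treated injury as known from admission would credit those days to the injured group, which is immortal-time bias.

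**The case against.** The strongest defence is that a separate statistical analysis plan may fix the number of days, and that such detail is often left there. This carries some weight, but the protocol itself states both the endpoint definition and the model, under its own analysis-plan heading, and the two do not fit together. That is a definition fixed badly, not merely a detail deferred.

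A second defence is that the authors may intend one logistic model per binary item, with stay described separately. The data list uses the items only as examples, and the Statistical analysis section does not repeat the word composite. This is plausible, and the repair would then be very small, but it does not rescue the endpoint as defined. Stay taken alone still could not enter a logistic model without a cut-off.

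Two parts of the defence stand. The t or Mann-Whitney tests could already describe stay by group, so a reader should not infer that the plan has no means of comparing it. And since the remaining components can be read as yes/no, a reader should not infer that secondary objective 1 as a whole cannot be analysed.

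A reader might also infer that the false-positive rate is inflated. In a null simulation (500 injured, 1500 uninjured, log-normal stay with assumed medians of 6 to 14 days, other components in 20% to 90% of patients), each single cut-off gave p<0.05 in about 5% of studies. At least one did so in 8–10% with two candidate cut-offs, 9–13% with three and 10–17% with five. The documents do not support using this as a finding. They nowhere say that several cut-offs will be tried and the most favourable kept, the rates are all assumed, and the test was an unadjusted comparison of proportions, not the planned multivariable model.

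**Conclusion.** The point holds in a narrow form. Secondary endpoint 1 contains a duration without a cut-off and is assigned a model that needs a yes/no outcome, so the composite cannot be coded as defined. This rests on the text alone. Depending on the unstated rule, the composite event rate could lie anywhere from the rate of the other components to 100%; any narrower figure depends on assumed stay and event rates.

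It should be fixed, but its reach is limited to one component of one secondary endpoint in a study that calls itself a pilot. Including drug use in the composite is not part of the defect. It fits the stated hypothesis of "higher incidence of in-hospital complications and need for escalation of therapies" and is the sponsor's choice.

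**What to change.** Remove length of hospitalization from the binary composite in Secondary endpoints, item 1, and keep logistic regression for the remaining components.

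Report stay separately, for example as time to discharge alive with in-hospital death as a competing event, because an early death also ends the stay. Handle the exposure in one of two ways:

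- Enter injury as a time-varying covariate from the first raised hs-cTnI. A cause-specific hazard model suits this. It needs dated troponin values, which the listed laboratory data would have to supply.
- Classify injury from the admission value. This is simpler, but inclusion requires only one troponin at some point in the stay, so patients without an admission value would be left out.

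Alternative: keep the component, with a cut-off for prolonged stay fixed before outcome data are examined. This takes one sentence. It loses information by dichotomising stay, and it keeps in the outcome a component that itself affects the chance of being classed as injured.

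Reporting each component beside the composite is optional. The protocol already plans this for the 12-month events ("both as incidence of the composite and as incidence of each individual components"), but the defect does not require it here.

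The cost of the main option is one reworded endpoint and one extra model, on data already listed under Variables and procedures.
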